#### **14) Sample size:**

A widely used programmatic measure of acceptable adherence is that patients are known to have taken at least 80% of their scheduled doses. This is particularly important early in treatment. We therefore define an adherent patient as one who is observed to take over 80% of their treatment and will compare the proportion of patients who are adherent in each arm over the first 2 months from randomisation as the primary outcome.

We have examined the power implications of a range of realistic differences in the primary outcome with 90% power at the 5% significance level (2 sided) with equal numbers in intervention and control arms of a superiority trial (table 1).

We have reviewed adherence data from Cohort review of TB patients and the VOT pilot and this suggests the 3rd or 4th scenarios are realistic.

Table 1 – Sample size needed at differing estimates of adherence and effect size.

	50% vs 70%	40% vs 60%	65% vs 80%	60% vs 75%
Intervention	121	126	181	200
Control	121	126	181	200
Total	242	252	362	400

We will aim to recruit 400 participants into the trial over a two year period.

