**8) Description of trial design.**

The TB Reach VOT trial is designed as a randomised, controlled, analyst blinded multicenter superiority trial with two parallel groups (VOT and DOT) with a 1:1 allocation and a primary endpoint of 80% of doses being observed over a 2 month period.

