## 12) Outcomes

### *Primary Outcome Measure:*

Proportion of participants having more than 80% of scheduled VOT/DOT sessions successfully completed in the 2 months following randomisation (binary aggregation) in participants with a minimum of 6 weeks follow up data.

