## **Statistical methods**

### **20a) Statistical methods for analysing primary and secondary outcomes.**

Characteristics of those randomised and those not randomised due to refusal or exclusion criteria will be compared. Baseline characteristics of those randomised to intervention and control arms will be compared to check for balanced randomisation. An intention to treat analyses will be used. Categorical outcomes will be compared across groups using the chi-square test or Fisher's exact test as appropriate. Continuous variables will be compared across groups using the Wilcoxon rank-sum test.

For some DOT schedules weekend doses are planned to be self-observed due to difficulty in providing DOT at the weekend. For the primary outcome these doses will not be considered in the denominator of scheduled doses, however, as this is a valuable advantage of VOT, secondary analyses will include these weekend doses as part of the treatment schedule). When participants are in hospital their dose will be considered to have been observed. When participants are in prison or custody the dose will be considered to have been observed if it can be verified with offender health that they were aware of the treatment regime. When patients are out of the country VOT participants will be encouraged to continue to take VOT clips which can either be submitted via a wifi connection or will automatically submit on return to the UK. Doses due during time abroad will not be considered as part of the primary outcome for either arm, but will be included in the secondary analyses to explore the potential value.

Patients who cross-over trial arms (see section 11b) prior to the end of 2 month follow up will be considered a failure for the primary outcome.

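### The recruitment target of 400 equals the number that must be analysed for 90% power at 60% v 75%, yet the primary outcome is limited to participants with at least 6 weeks of data

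*Protocol*

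**What the plan says.** Section 14 sizes the trial "with 90% power at the 5% significance level (2 sided) with equal numbers in intervention and control arms of a superiority trial". Table 1 gives four scenarios, with 121, 126, 181 and 200 participants per arm. The protocol judges that the third (65% v 80%, 362 in total) and the fourth (60% v 75%, 400 in total) "scenarios are realistic". The target then follows: "We will aim to recruit 400 participants into the trial over a two year period". No allowance for loss or exclusion is stated. Section 8 describes "two parallel groups (VOT and DOT) with a 1:1 allocation".

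Section 12 sets the primary outcome as the proportion with more than 80% of scheduled sessions completed in the 2 months after randomisation, "in participants with a minimum of 6 weeks follow up data".

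Section 20a adds two statements on analysis: "An intention to treat analyses will be used", and "Categorical outcomes will be compared across groups using the chi-square test or Fisher's exact test as appropriate".

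Three other rules bear on who is scored:
- Section 11b treats participants who do not take up their allocated observation as failures of that arm.
- Sections 11b, 20a and 20c count a switch of arm before 2 months as a failure.
- Section 18b records sessions after loss to follow-up as not completed, for participants who have not withdrawn.

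**The concern.** The number recruited and the number analysed are different quantities once the outcome definition removes people after randomisation. Section 14 treats them as the same. If the tabulated 400 is the number needed for analysis, each participant dropped by the 6-week rule takes the trial below its stated power at 60% v 75%, the scenario that produced the target.

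What is at stake is the accuracy of the stated power. A reader of the final report would take 90% as the design power for a 15-point difference, when the figure depends on an unstated share of participants being evaluable. The 6-week restriction also sits beside rules that score poor engagers as failures, so the protocol leaves unclear how many participants the restriction would remove.

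**Working it through.** **Inputs.** Two-sided 5%, 90% power, equal arms and the four pairs of rates come from section 14. The 1:1 allocation is in section 8 and the chi-square test in section 20a. Exclusion rates of 0%, 5%, 10% and 20% are assumptions, applied equally to both arms.

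**Step 1: reproduce Table 1.** The unpooled two-proportion formula is

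n per arm = (1.960 + 1.282)² × [p1(1 − p1) + p2(1 − p2)] / (p1 − p2)²

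For 60% v 75% this is 10.51 × (0.24 + 0.1875) / 0.0225 = 199.6, hence 200.

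| Scenario | Formula, per arm | Table 1, per arm |
|---|---|---|
| 50% v 70% | 120.8 | 121 |
| 40% v 60% | 126.1 | 126 |
| 65% v 80% | 181.0 | 181 |
| 60% v 75% | 199.6 | 200 |

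The table is reproduced (126.1 is printed as 126, which is immaterial). The formula has no loss term. A pooled-variance formula gives 203 per arm for 60% v 75% and a continuity correction gives 216, so neither explains the printed 200. The 400 contains no hidden allowance.

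**Step 2: compare target with requirement.** The target is 400. The number to be analysed at 60% v 75% is 2 × 200 = 400, so the margin is zero. At 65% v 80% it is 2 × 181 = 362, so the margin is 1 − 362/400 = 9.5%.

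**Step 3: power with 400 randomised.** With a share d excluded, the number analysed per arm is 200 × (1 − d). Power is exact for the Pearson chi-square test without continuity correction: binomial probabilities are summed over all pairs of counts for which the test is significant at two-sided 5%.

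| Excluded (assumed) | Analysed per arm | Power, 60% v 75% | Power, 65% v 80% |
|---|---|---|---|
| 0% | 200 | 89.7% | 92.4% |
| 5% | 190 | 88.2% | 91.1% |
| 10% | 180 | 86.5% | 89.7% |
| 20% | 160 | 82.2% | 85.9% |

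As a cross-check, the pooled normal approximation at 60% v 75% gives 89.6%, 88.0%, 86.3% and 82.0%.

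**Step 4: who the 6-week rule could remove.** If the scoring rules in sections 11b, 18b and 20a take precedence over section 12, then non-uptake, switches of arm and loss to follow-up without withdrawal all stay in the analysis. What remains exposed is a smaller group, such as withdrawals and participants whose diaries are not returned. If section 12 takes precedence, someone who never starts or is lost in the first weeks could be dropped even though another section calls that person a failure. The protocol does not say which reading applies.

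**The case against.** The strongest reply is that the protocol keeps most poor engagers by scoring them. It states intention to treat, counts non-uptake and cross-over as failures, and treats sessions after loss to follow-up as missed. It excludes before randomisation anyone with under 2 months of treatment left, and section 20c foresees multiple imputation for missing data. On that reading few are removed and the cost is small: about 1.4 points of power at 5% excluded and about 3 points at 10%. The protocol also names two realistic scenarios and adopts the larger sample size, so at 65% v 80% there is room for exclusions.

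Most of this stands. It limits the size of the problem and rules out a claim that the trial is seriously underpowered. It does not remove the point: section 18b covers only those who have not withdrawn, the 6-week restriction stands in the definition of the primary outcome itself, and no section says which rule prevails.

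Two stronger readings are tempting. A reader might infer heavy exclusion from section 15, which describes the population as difficult to engage. That remark justifies same-day recruitment and concerns people lost before enrolment. A reader might also infer that recruitment cannot exceed the target, since the assumptions multiply to 420 × 0.95 × 0.75 × 2/3 × 2 = 399. The same section says that true eligible numbers will be higher, so this does not show that there is no room. Nor does any such surplus supply an allowance, because the stated aim remains 400.

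**Conclusion.** The point holds in a limited form. The target carries no allowance for the exclusion that section 12 builds in, so 90% power at 60% v 75% is reached only if everyone randomised is analysed. The shortfall cannot be fixed from the protocol, which gives no exclusion rate. On assumed rates, power at 60% v 75% is 88.2% with 5% excluded, 86.5% with 10% and 82.2% with 20%. At 65% v 80% it stays at about 90% or better up to 10% excluded.

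A reader might infer that the trial fails to deliver its power in general. The documents do not support that: it is not so for one of the two planning scenarios at modest exclusion, and the scoring rules may leave only a small group excluded. A reader might also suppose that counting non-starters as failures lowers both planning rates and costs further power. That is a separate question, and it depends on whether the cohort review and pilot data behind those rates already counted such participants, which the protocol does not show.

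This is not a matter that can be left to an analysis plan, because the target, the power claim and the restriction are all fixed in the protocol.

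**What to change.** 1. In section 14, keep 400 and state power for both realistic scenarios as conditional on the share analysed. For example: with 400 randomised, power at 60% v 75% is about 90% if all are analysed and about 86% if 10% are not; at 65% v 80% the figures are about 92% and about 90%. Say that the exclusion rate is assumed.
2. Reconcile the 6-week restriction in section 12 with sections 11b, 18b and 20a. State that participants whom those sections score as failures, or whose later sessions they record as not completed, remain in the primary analysis and are not dropped for having under 6 weeks of data. Say who, if anyone, the restriction still removes.

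The cost is a few sentences and a slightly less favourable stated power. No extra patients are needed.

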#### **15) Recruitment Strategies for achieving adequate participant enrolment to reach target sample size.**

Recruitment relies on conducting the study in multiple centres. We have focussed recruitment of clinics based on existing good relationships and high numbers of cases eligible for DOT. We are also approaching Birmingham clinics to increase numbers.

Based on the following assumptions we expect to be able to recruit 400 patients over a 2 year period.

Assumptions:

The annual number of eligible patients at each clinic will be similar to the annual number of patients reported to national enhanced surveillance in 2010 and 2011 as having social risk factors (homelessness, problem drug or alcohol use or history of imprisonment) but not on DOT, plus the number of patients already on DOT. This averaged at 420 eligible per annum.

It was also assumed that:

95% of those eligible for DOT are also eligible for the trial

Clinics attempt to recruit 75% of those eligible

2/3 of those who are approached agree to participate (based on pilot data VOT acceptance rates)

Note – As MDRTB patients with twice daily treatment are now not included in the randomisation we have not included MDRTB in the estimates. The true numbers of eligibles will be higher as we have ignored, previous history of TB and history of poor adherence, also this is based on incident eligible cases whereas we will also be recruiting patients who are currently on DOT.

We will initially attend outpatient appointments to induct clinics and promote the trial. We will visit clinics monthly for quality control visits.

Another strategy for achieving good recruitment is an emphasis on recruiting patients on the day the study is first introduced to them. As this is a hard – to – engage group delaying this could lead to substantial drop-out.

## **Methods: Assignment of interventions (for controlled trials)**

Allocation:

16a) Sequence generation

We will use computer generated randomisation by minimisation to ensure balance across study sites and stage of treatment at which recruitment took place 1) at start of treatment; 2) after start but within first 2 months of treatment; 3) After first 2 months of treatment.

This will ensure that treatments are balanced within the two strata.

### **16b - Allocation concealment mechanism**

Randomisation will be commissioned from SealedEnvelopeTM (<http://www.sealedenvelope.com/>) and conducted centrally using an integrated internet/telephone randomisation service. Clinics will randomise using the internet or telephone service, or contact the study centre who will randomise and pass on the allocation to the clinics. The systems also check for consent, study inclusion and exclusion criteria before allowing randomisation (Randomisation Form - Appendix 6).

### **16c) Implementation**

The allocation sequence will be generated by SealedEnvelopeTM. Participant enrolment and assignment to intervention will be done by the study nurse or clinic nurse (see Participant timeline – section 13)

### **17a) Blinding (masking)**

It is not possible to blind participants or care providers to the intervention.

It is also not possible to blind those undertaking interviews at 2 and 6 months, as these questions include information on participant time taken to have DOT or VOT which will make the allocation obvious.

Data analysis will be blinded to the allocation for the primary outcome by ensuring the statistical files for analysis are prepared blind to the intervention.

**17b) If blinded, circumstances under which unblinding is permissible** – not applicable.

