### **11a) Interventions for each group**

VOT: Daily submission of VOT clip using dedicated smartphone with pre-loaded app allowing upload to a secure server. Participants will be trained on how to lay out each drug on a labelled laminated medication sheet with a space for each drug and take each drug type individually saying either the name of the drug or the colour of the pills, size, and the number taken. Participants will be asked to show their mouth is empty by opening their mouth and sticking out their tongue and finally be asked to report any symptoms from a list of key side effects (which will be printed on the reverse of the laminated medication sheet – **Appendix 1 & 2**). Any reported or observed side effects will be addressed by study nurses as indicated in **Appendix 3**.

Training will include submission of test videos.

VOT clips will be submitted automatically as soon as the phone is connected to a cellular data network (data plan provided with phone) or wireless network.

VOT clips will be read by a study nurse/VOT observer daily during weekdays with weekend clips read on Mondays.

No incentives or travel costs will be provided but participants will be able to make use of study smartphone for e-mails, domestic telephone calls and internet searches (limited data downloads apply).

After any missed dose of VOT the observer will attempt to contact the patient by telephone to find out what the problem is and encourage submission of further video clips. If this is a technical problem that cannot be resolved over the phone a visit will be arranged to resolve this. If they are unable to contact them within 24 hours of a missed dose they will contact the case manager to discuss.

DOT: A trained health professional, or responsible lay person supported by a trained health professional, provides the prescribed medication and observes the patient swallowing every tablet prescribed (or for some schedules observing doses during weekdays with self-administered therapy at weekends). Organised by clinic according to usual practice – may be

- a) clinic based
- b) community based working with a responsible professional such as a hostel worker or pharmacist
- c) through a DOT worker outreaching DOT.

Clinics may choose to use incentives and provide travel costs as per normal practice

After each missed dose of DOT the case manager will attempt to contact the patient by telephone to find out what the problem is and encourage re-engagement.

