Day zero. Time 0-5 mins – Clinic nurse discusses the recommendation that the patient be treated with DOT and the possibility of being involved in a study of how best to observe treatment (face to face) or using video observed therapy. (A, B, C)

Day zero – Time 5-25 minutes - Clinic nurse provides patient information sheet to patient and allows them to assess whether they wish to receive further information. (A, B, C)

Day zero – Time 25-50 minutes –Clinic nurse (A) or study nurse (B or C) explain the study, seek written consent, randomise and arrange onward care.

Day zero – Time 50-60 minutes - study nurse (A) or clinic nurse (B, C) collect baseline data largely populated from existing clinical data/care records.

Day zero Time 60 minutes -120 minutes (A & B) – Training in use of VOT and provision of smart phone.

Day one (or first working day after day zero) – (C) VOT training up to 1 hour at patients home or at clinic depending on patient preference.

Day one (A & B) or two (C) – VOT arm – patient attempt to submit VOT clip unaided, study team liaises and arranges further training if necessary.

Day one (or first scheduled DOT appointment) – patient begins attending for DOT.

[figure not shown]
0-2 months – regular DOT/VOT with adherence data collection and monitoring of side effects.

2 months – Study team contact participant by telephone to complete follow up questionnaire covering satisfaction with DOT or VOT, Time spent on DOT or VOT, Employment and quality of life, periods of time spent away from home.

Regular out-patient appointment closest to 2 months clinic nurse requests sputum sample to test for culture conversion at local laboratory.

6 months or end of treatment - Study team contact participant by telephone to complete end of follow up questionnaire covering satisfaction with DOT or VOT, Time spent on DOT or VOT, Employment and quality of life, periods of time spent away from home. For patients still requiring onward care the study will liaise with the clinic and Find&Treat to organise continuing DOT or VOT.

Schematic of participant timeline

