## **Methods: Data collection, management, and analysis**

### **18a) Data collection methods**

Recruitment data (CRF 1 - Appendix 7): Recruiting clinics will collect anonymous data on the characteristics of patients who were approached for the trial but declined to participate using a study recruitment log sheet. This will include age, sex and factors that make them eligible for DOT.

Baseline Data (CRF 2 – Appendix 8): Study or clinic nurses will collect baseline data at the time of initial recruitment. This mainly consists of data already routinely collected by clinics, covering patient demographics, disease categorisation and factors that make them eligible for DOT. It will also include the validated EQ-5D quality of life scale and information on employment status and approximate weekly salary

VOT/DOT diary (CRF 3 – Appendix 9):

This will be recorded by the DOT observer at the time of the scheduled session and by the VOT observer at the time of reading scheduled video clips. DOT/VOT observers will be trained to complete (CRF 3 – see section 18a) consistently. CRF3 will be faxed/emailed on a weekly basis to the study centre with the study centre following up with DOT observers when weekly forms are not returned. CRF3 will be completed directly at the study centre on the VOT reading system.

The VOT reading system includes: fields to identify when doses are scheduled; when clips are submitted and read and the following categorisation of clips:

Patient took meds?

- Y (Yes, all meds)
- P (Probably)
- S (Yes, some meds)
- N (No meds taken)
- U (Unable to tell)
- DNA / Did not send clip

This data will be used for the primary outcome and secondary adherence outcome measures.

The system also collects additional data on video and audio quality. The system collects data on geo-location at the time of recording. This will be collected if the participant provides separate consent for this.

DOT: A DOT diary will be completed by DOT observers showing when doses are scheduled to be observed, whether or not the participant attended, when they attended and whether they took the medicines categorised as above.

Patient 2 and 6 month follow up (CRF 4a & 4b – Appendix 10): The study team will contact the participant by telephone to complete a 5 minute questionnaire covering

- Quality of Life (EQ5D)
- Participant satisfaction (Likert scale)
- Participant resource use for DOT/VOT (Participant time, missed work)
- Employment
- Hospitalisation

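### Section 17a leaves the whole follow-up interview unblinded for a reason that covers only the arm-specific items, an avoidable risk for EQ-5D and the other secondary interview outcomes

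*Protocol*

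**What the plan says.** Section 17a first accepts that "It is not possible to blind participants or care providers to the intervention". It then extends this to the interviewers, with a single reason: "It is also not possible to blind those undertaking interviews at 2 and 6 months, as these questions include information on participant time taken" for either mode of observation, which would disclose the arm. The only blinding it promises is of the analysis files for the primary outcome.

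On the content of the call, section 18a says "The study team will contact the participant by telephone to complete a 5 minute questionnaire covering" quality of life (EQ-5D), satisfaction, participant resource use, employment and hospitalisation. Section 12 lists the same items as secondary outcomes. Section 13 describes the 2-month call as "Study team contact participant by telephone to complete follow up questionnaire covering satisfaction with DOT or VOT", followed by time spent, then employment and quality of life.

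On who delivers each intervention, section 11a says "VOT clips will be read by a study nurse/VOT observer daily during weekdays with weekend clips read on Mondays", and section 18a adds that for VOT "CRF3 will be completed directly at the study centre on the VOT reading system". VOT observers telephone after missed doses (11a), arrange retraining (11b) and may send encouragement (11d). DOT is organised by the clinic, and its case manager follows up missed doses (11a, 11b).

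**The concern.** A reason that holds for one or two questions is used to leave the whole interview unblinded. An item that reveals the arm cannot influence answers already recorded, so it gives no ground for collecting EQ-5D, employment and hospitalisation from a caller who knows the allocation.

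The caller's position may also differ between arms. The term study team covers both those who telephone participants and those who help them with VOT. A VOT participant may therefore be answering someone from the team that supports their treatment, while a DOT participant describes a clinic service to people who mostly do not run it. Any resulting courtesy or interviewer effect would tend to favour VOT. Quality of life, satisfaction and cost effectiveness are stated objectives (section 7), and blinding the analyst cannot remove a bias that entered at data collection.

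**Working it through.** **1. Which items does the stated reason cover?** Setting section 17a beside the item lists in sections 12, 13 and 18a:

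- Time spent on DOT or VOT (resource use): reveals the arm. This is the reason 17a gives.
- Satisfaction: reveals the arm as section 13 words it, though 17a does not mention it.
- EQ-5D, employment, hospitalisation: none requires the mode of observation to be named.

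Three of the five content areas in 18a therefore fall outside the reason given.

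**2. Is the order protected?** Sections 12 and 18a list EQ-5D first. Section 13 lists satisfaction and time before quality of life. These are lists of content; none of them fixes the order of questions.

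**3. Is the caller separated from VOT delivery?** Sections 13 and 18a name only the study team. Section 13 uses the same term for those who liaise with a VOT participant after the first unaided clip and arrange more training. No sentence excludes the participant's own VOT observer or trainer, and none says that this person makes the call.

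**4. Scale, by illustration.** The protocol gives no figure to reproduce on this point: no SD for EQ-5D or satisfaction, no interview response rate and no size of interviewer effect. The inputs below are therefore assumptions, apart from 200 per arm, which is half the target of 400 in section 14.

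For a spurious shift of d standard deviations in one arm, no true effect and n analysed per arm, the shift of the test statistic is d / √(2/n), and the chance of a significant result is P(|Z + shift| > 1.96).

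| d (assumed) | n = 150: shift | n = 150: chance | n = 200: shift | n = 200: chance |
|---|---|---|---|---|
| 0.1 | 0.87 | 13.9% | 1.00 | 17% |
| 0.2 | 1.73 | 41.0% | 2.00 | 52% |
| 0.3 | 2.60 | 73.8% | 3.00 | 85% |

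For example, √(2/150) = 0.1155 and 0.2 / 0.1155 = 1.73. Without a shift the chance is 5%. The formula compares means by a normal approximation, whereas section 20a specifies the Wilcoxon test for continuous outcomes and chi-square or Fisher's test for categorical ones, so the percentages are approximate even under their own assumptions.

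**The case against.** The strongest reply is that 17a is true as written. It speaks of interviewers, not items, and in one short call that covers time and satisfaction the interviewer will learn the arm. This stands for those two items and for everything asked after them. It does not stand for what can be recorded before them.

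Other objections stand in whole or part:

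- A reader might infer that VOT observers make the calls, or that the study team delivers VOT and has no part in DOT. The documents say neither. Study nurses may recruit and randomise patients to both arms (section 13), the centre follows up missing DOT diaries (18a), Find&Treat is a study setting (section 9), and DOT may be given by outreach (11a). The difference between arms is an inference at team level.
- Participants know their arm and report EQ-5D and satisfaction themselves. Blinding the caller removes only the interviewer's part of any bias. Satisfaction cannot be blinded in any order; for it, the gain comes from a caller not involved in that participant's VOT.
- The courtesy argument is weaker for EQ-5D, which does not rate the provider.
- Someone who made the 2-month call, or randomised the participant, already knows the allocation at the next call. Participants may also switch mode under 11b, which blurs the contrast by 6 months.
- CRF 4a/4b is an appendix not available here and may already place EQ-5D first. If so, that part of the fix is done and only the wording of 17a needs to follow.

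**Conclusion.** The point holds as an avoidable risk of unknown size, confined to the secondary outcomes from the telephone interview. Section 17a's reason supports unblinded time and satisfaction items. It does not support giving up on EQ-5D, employment and hospitalisation, and the protocol text contains no safeguard on item order or choice of caller.

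It would go too far to say that these outcomes are biased: the documents give no evidence of a shift or of its size. The 14%, 41% and 74% figures rest wholly on an assumed 150 interviews per arm and assumed shifts. They show how sensitive a comparison of this size is, and they attribute the whole shift to the interviewer, part of which could be self-report bias that would survive the fix. Nor does the point touch the primary outcome, which comes from the VOT/DOT diary (CRF 3), or the sample size. That EQ-5D would carry a bias into cost effectiveness is plausible given the objectives in section 7, but the protocol does not say how EQ-5D will be used there.

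Because the change is cheap and the risk would tend to favour VOT, it is worth making.

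**What to change.** In section 17a and CRF 4a/4b:

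1. Limit the statement that blinding is not possible to the time and satisfaction items.
2. Record EQ-5D, employment and hospitalisation before any item that names DOT or VOT, with satisfaction last.
3. Give callers a contact list without allocation.
4. Have the call made by an existing team member who is not that participant's VOT observer or trainer and, where feasible, did not make that participant's 2-month call.
5. State the remaining limitation: participants are unblinded, and satisfaction is collected unblinded.

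The cost is a fixed question order, a caller rota and less flexible scheduling. This assumes that the study team has more than one person able to telephone; the protocol gives no staffing figures. The sample size, the primary analysis and patient care do not change. Protection remains partial, since some participants will reveal their arm before the DOT/VOT items are reached.
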